The PI for this study is on faculty in the MGH Division of General Internal Medicine and is a staff physician at MGH Revere. The proposed trial will be funded by the PI's Career Development (K23) Award from the National Institute on Drug Abuse at the National Institutes of Health, and by a grant to the PI from the MGH Executive Committee on Research Claflin Distinguished Scholars Award.

II. Specific Aim

Research Aim 1: To test, in a 4 arm pilot randomized controlled trial ($N=50/group$), the effect of delivering behavioral smoking cessation content by text message and mailed nicotine replacement therapy on self-reported quit attempts (intentional non-smoking for ≥ 24 hours), pharmacotherapy adherence, and smoking abstinence at the end of treatment.

Hypothesis 1: A 12 week text messaging intervention (up to 30 days pre-quit through 8 weeks post-quit) providing behavioral support will increase the proportion of smokers making a quit attempt compared to smokers receiving no text messaging.

Hypothesis 2: A 12 week text messaging intervention will increase adherence to NRT compared to subjects receiving only 2 weeks of NRT as measured by: (a) duration of NRT use in days and (b) total mg of NRT used.

[figure not shown]
Hypothesis 3: A 12 week text messaging intervention will increase the rate of *biochemically confirmed* past 7-day point prevalent tobacco abstinence at end of treatment compared to subjects receiving no text messaging intervention.

Hypothesis 4: A 12 week text messaging intervention will increase the number of days not smoking compared to subjects receiving no text messaging intervention.

Hypothesis 5: A 12 week text messaging intervention will decrease the number of cigarettes smoked compared to subjects receiving no text messaging intervention

Study Design

Figure. Pilot randomized controlled trial schema

III. SUBJECT SELECTION

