The sample of smokers enrolled in the study will be characterized on baseline measures from the EHR and compared to the population of smokers whom we attempted to contact in order to determine the sample's representativeness to the target population. Variables include demographics, medical history, and practice characteristics. We will also compare baseline characteristics collected from the EHR and from baseline interviews between the 4 randomized groups to determine the success of randomization. The primary outcome analysis will be conducted as intention-to-treat, comparing the primary outcome using chi-square analysis or multiple logistic regression analysis if any baseline factor is significantly imbalanced by group ($p<0.05$) as independent variables. The 4 arm design allows for analysis as a factorial design. We will first test for interaction between the NRT and TM interventions and if no interaction is detected we will test the effect of text messaging using both TM and TM+NRT arms compared to BA and NRT arms. If interaction is present, we will compare the TM arm to BA for our primary analysis. We will secondarily compare the groups in terms of self reported 7 day PPA, biochemically confirmed abstinence, number of days not smoked, use of ≥ 1 evidence based treatments, and cigarettes per day using chi-square or t-tests or logistic or linear regression if groups are imbalanced. We will also compare the TM+NRT group with the NRT group in terms of total days of medication used and total mg of medication used over 2 weeks using linear regression. We will conduct stratified analyses of the primary outcome, 7 day PPA, treatment use and days not smoked by readiness to quit in the next 30 days.

Sample size

Hypothesis 1: A 12 week text messaging intervention (up to 30 days pre-quit through 8 weeks post-quit) providing behavioral support will increase the proportion of smokers making a quit attempt compared to a control group receiving brief advice.

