The sample size for this pilot study is selected to adequately estimate recruitment rates, retention, and to get a preliminary estimate of prevalence of clinical outcomes. We anticipate we can recruit 200 patients by proactive outreach over 12 months. With 50 patients per group and 25% loss to follow-up we will have 81% power to detect a relative risk of self-reported ≥ 24 hour quit attempts of 1.8 for text messaging versus brief advice groups. We base this estimate on meta-analyses of smoking cessation text messaging trials, mostly from community settings or school-based settings, report a relative risk of 1.4 for 7-day point prevalence abstinence and 1.6 for prolonged abstinence measured at six-months.^{8,71}

Hypothesis 2: A 12 week text messaging intervention providing personalized, tailored behavioral support and advice about using nicotine replacement therapy (NRT) plus 2 weeks of NRT mailed to the participant will increase adherence to NRT compared to subjects receiving only 2 weeks of NRT as measured by duration of NRT use in days.

For our secondary outcome of medication adherence, we estimate patients randomized to the NRT will use a mean 9 days of medication based on the offer to mail them 2 weeks of medication for free.⁷² With this sample size, we also have 80% power to detect an increase in days of NRT use from 9 to 12 days in NRT vs. NRT+TM.

Hypothesis 3: A 12 week text messaging intervention will increase the rate of *biochemically confirmed* past 7-day point prevalent tobacco abstinence at end of treatment compared to subjects receiving no text messaging intervention.

We do not expect to have power to detect cessation in this pilot study. With 100 subjects and 25% loss to follow-up we will have 80% power to detect an increase from 6% among the BA & NRT groups to 22% in TM & TM + NRT groups.

Regardless, this pilot study aims to generate an estimate of effect size on cessation at 12 weeks for further studies.

Hypothesis 4: A 12 week text messaging intervention will increase the number of days not smoking compared to subjects receiving no text messaging intervention.

Assuming $\alpha=0.05$ and 25% loss to follow-up, leaving 75 patients, we have 68% power to detect an increase in days not smoked from 0.2 in groups receiving no text messaging (BA & NRT) to 1 in groups receiving text messaging (TM & TM + NRT) assuming a standard deviation of 2.

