Hypothesis 5: A 12 week text messaging intervention will decrease number of cigarettes smoking compared to subjects receiving no text messaging intervention.

Assuming $\alpha=0.05$ and 25% loss to follow-up, leaving 75 patients, we have 75% power to detect a decrease in cigarettes smoked per day from 15 among those receiving no text messaging (BA & NRT) to 12 in groups receiving text messaging (TM & TM + NRT) assuming a standard deviation of 7.

VII. RISKS AND DISCOMFORTS

- a. Complications of surgical and non-surgical procedures
Not applicable

- b. Drug side effects and toxicities

Side effects of the nicotine patch may include itching, burning or tingling when the patch is applied. This usually goes away within an hour, and is a result of nicotine coming in contact with the skin; redness or swelling at the patch site for up to 24 hours; dizziness; headache; upset stomach; vomiting; diarrhea; and palpitations.

Side effects of the nicotine lozenge include mouth irritation or ulcers, in addition to nicotine-related side effects of dizziness; headache; upset stomach; vomiting; diarrhea, and palpitations.

- c. Device complications/malfunctions

Errors in the text messaging platform include skipped text messages or failure to respond to a user-initiated text message. While this may affect the fidelity and clarity of the text messaging intervention we do not think this poses a risk to subject health or well-being.

- d. Psychosocial (non-medical) risks

i). Psychological discomfort: Quitting smoking can be psychologically stressful and, at times, physically uncomfortable because of cravings and nicotine withdrawal symptoms.

ii). Risks to privacy: Text messages are not a secure messaging platform. Any person using the subject's designated phone can see the messages which may include information about quitting

smoking. It may be psychologically stressful for subjects if other persons see text messages disclosing their smoking status. We will also collect and record identifying information (e.g. name, date of birth and social security number) and ask about potentially sensitive topics (smoking history, depression screening questions, anxiety screening questions, alcohol and substance use disorder screening questions). Name, telephone number, and smoking status will be shared with the text messaging vendor. The vendor underwent risk assessment by Research Information Security to evaluate their data security practices.

- e. Radiation risks
Not Applicable

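### An interaction pretest with no stated level chooses the primary comparison; type I error rises to about 6.4–7.0%, and H1 is powered only for the fallback contrast

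*Combined protocol and SAP*

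**What the plan says.** The Data analysis part of Section VI sets a two-step rule for the primary outcome, self-reported quit attempts. Step one: "We will first test for interaction between the NRT and TM interventions and if no interaction is detected we will test the effect"; this is the text messaging effect, with TM and TM+NRT together against BA and NRT together. Step two: "If interaction is present, we will compare the TM arm to BA for our primary analysis". No level, scale or statistic is given for the interaction test, and no adjustment of the final alpha. The only threshold in that text, p<0.05, concerns baseline imbalance.

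For the other text-messaging pair, the section states "We will also compare the TM+NRT group with the NRT group in terms of total days of medication used" and total mg. It does not name that pair for quit attempts.

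Hypothesis 1 is worded in two ways. In Section II, text messaging "will increase the proportion of smokers making a quit attempt compared to smokers receiving no text messaging", which is the pooled contrast. Under Sample size it is "compared to a control group receiving brief advice". The H1 power statement (50 per group, 25% loss, 81% power) concerns a relative risk of ≥24-hour "quit attempts of 1.8 for text messaging versus brief advice groups". H3 to H5 are powered on pooled arms: H3 "to detect an increase from 6% among the BA & NRT groups to 22% in TM & TM + NRT groups", H5 "from 15 among those receiving no text messaging (BA & NRT) to 12 in groups receiving text messaging", and H4 likewise.

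**The concern.** The two branches answer different questions: the effect of TM averaged over NRT, or the effect of TM without NRT. The data choose which is primary. TM versus BA shares data with the interaction contrast, so trials in which a chance interaction appears are also those in which TM versus BA tends to be extreme. Testing each branch at 5% then gives an overall error above 5%.

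Power is affected too. The text program carries NRT-adherence messages (Section V.a), and Hypothesis 2 expects TM to raise NRT use, so a larger TM effect alongside NRT is plausible. In that case a detected interaction moves the primary test to the two arms without mailed NRT, where the effect is small, and no named contrast then tests quit attempts in TM+NRT versus NRT. Finally, the branch used when no interaction is found has no H1 power statement.

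**Working it through.** **Inputs from the protocol.** Four arms, 1:1:1:1, 50 per arm, 25% loss: 37.5 per arm (37 in the simulations) and 75 per side when pooled. Alpha 0.05 is stated only for H4 and H5. **Assumed:** two-sided final tests at 0.05, an interaction level of 0.05 to 0.20, and all quit-attempt rates.

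**1. The plan's H1 figure.** The control rate is not stated, so 81% cannot be reproduced directly. With the pooled-variance normal formula,

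power = Φ{[Δ − 1.96·√(2p̄(1−p̄)/n)] / √[(p₀(1−p₀)+p₁(1−p₁))/n]},

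n = 37.5 per group and RR 1.8, solving for 81% gives p₀ = 0.40 and p₁ = 0.72:

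- p̄ = 0.56 and Δ = 0.32. The two standard errors are √(0.4928/37.5) = 0.1146 and √(0.4416/37.5) = 0.1085.
- (0.32 − 1.96×0.1146)/0.1085 = 0.88, so power is 81.0% (80.5% at n = 37, 81.5% at n = 38).
- The same rates at 75 per side give 98.2%.
- At 75 per side, 0.40 versus 0.63 (RR about 1.57) gives 81%.

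A pooled reading would also give 81% if the control rate were about 28%. The arithmetic alone therefore cannot settle which contrast was meant; the wording and the 50 per group point to TM versus BA. The other statements do reproduce as pooled, at 75 per side: H3 81.3% (stated 80%), H4 68.8% (68%), H5 74.7% (75%).

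**2. Type I error of the rule.** Let M be the pooled TM z-score and I the interaction z-score. With equal arm sizes and variances they are independent under the null, and the TM-versus-BA z-score is S = (M − I)/√2, so |corr(S, I)| = 1/√2 = 0.71. With interaction level a:

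type I error = (1 − a)×0.05 + a×P(|S| > 1.96, given a significant interaction).

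| Interaction level a | False-positive rate after a switch | Overall type I error |
|---|---|---|
| 0.05 | 33.8% | 0.95×0.05 + 0.05×0.338 = 6.4% |
| 0.10 | 25.1% | 0.90×0.05 + 0.10×0.251 = 7.0% |
| 0.20 | 17.2% | 0.80×0.05 + 0.20×0.172 = 7.4% |

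The maximum is about 7.5%, near a = 0.25. The middle column is the same excess viewed within the trials that switch, not a further error.

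**3. Simulation under the null.** 400,000 trials per scenario, logit-scale Wald interaction test at 0.05 (0.5 added to cells), then uncorrected chi-square. At 37 per arm and null rates of 20–60%, the rule rejects in 6.3–7.1% of trials and a fixed pooled chi-square in 5.0–5.9%. The rule thus adds about 1.3–1.4 points (1.8–2.0 at interaction level 0.10); the rest is discreteness of the chi-square test. At 38 per arm and a 50% rate the figures are 5.9% and 4.5%, again a gap of about 1.4 points.

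**4. Power, rule versus fixed pooled test** (37 per arm, interaction at 0.05, assumed rates):

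| Scenario (BA / TM / NRT / TM+NRT) | Rule | Fixed pooled |
|---|---|---|
| Synergy: 40 / 45 / 45 / 75% | 40% | 60% |
| TM works only with NRT: 38 / 38 / 38 / 68% | 29% | 47% |
| TM works only without NRT: 38 / 68 / 38 / 38% | 68% | 47% |
| Equal effects: 38 / 68 / 38 / 68% | 94.5% | 96.6% |

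In the synergy case about 35% of trials switch, and TM versus BA is then significant in about 2% of them. At 50 per arm the rule has 41% against 72%: more patients make a switch more likely, so the rule gains almost nothing.

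**The case against.** The rule is prespecified with both contrasts named, in a pilot sized mainly to estimate recruitment, retention and outcome prevalence. The excess is small: 6.4% at 0.05, the only threshold that appears anywhere in the documents. Section I.c describes testing the interventions alone and in combination against brief advice, and Section IV.c gives testing of text messaging alone as a purpose of the design, so TM versus BA has support of its own. Most of the power lost under synergy is correct non-rejection of a contrast whose true effect is small. With milder interactions the difference shrinks: 65% against 71% for 40/55/45/70%, and 65% against 60% in the rule's favour for 40/65/50/60%. The missing pooled power figure hides no shortfall, since that branch has the larger sample.

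Much of this stands. The excess is modest, neither approach has higher power in every scenario, and TM versus BA could legitimately be fixed as primary. It does not rescue the rule: prespecifying it does not hold its error at 5%, and a pretest still decides what the primary result estimates. The pooled contrast is the plan's own default branch and matches H1 in Section II and the contrasts used for H3–H5.

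**Conclusion.** The concern holds. As written, the rule rejects about 6.4% of the time under the null with an interaction level of 0.05 and 7.0% at 0.10, and the excess arises in the trials that switch. It loses substantial power if TM works mainly with NRT, gains if TM works only without NRT, and loses about 2 points if effects are equal. These figures rest on assumed interaction levels, two-sided 5% final tests and assumed quit-attempt rates. That H1 is powered for the fallback contrast is the natural reading of the text; with no control rate given, the 81% itself can be neither confirmed nor called wrong. If the back-solved 40% is right, the pooled branch has ample power (98% for RR 1.8) but the plan does not say so. This should be corrected; given the modest size and the pilot setting, it does not undermine the trial.

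**What to change.** - Make the TM main effect (TM and TM+NRT versus BA and NRT, with NRT in the model) the primary analysis whatever the interaction result.
- Report the interaction estimate with its confidence interval, and the TM effect on quit attempts within each NRT stratum (TM versus BA; TM+NRT versus NRT), as secondary.
- Under Sample size, word H1 against no text messaging, as in Section II, and rewrite its power statement for 75 versus 75 with the assumed control rate stated.

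Carried out as a Mantel-Haenszel test stratified by NRT, this gave 4.9–5.8% type I error in the simulations, with power of 60% (synergy), 48% (only with NRT), 47% (only without NRT) and 96.6% (equal effects).

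Two alternatives also hold 5% but fit the Section II hypothesis less well: fix TM versus BA as primary, or keep the rule, state the interaction level and test at a final alpha of about 0.038 (interaction at 0.05) or 0.034 (at 0.10).

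The cost is text only: two sentences of the Data analysis, the H1 wording and the H1 power paragraph. Arms and sample size do not change. The downside is lower power if TM works only without NRT (47% against 68% in the example above); the pooled estimate would then average unlike effects, which the stratum estimates would show.

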Rationale: In order to test the effect of text messaging on medication adherence, we need to have treatment groups receiving medication and medication plus text messaging. To deliver medication, mailed NRT, like text messaging, reaches patients outside of the busy office visit. Mailed NRT alone has also been shown to increase cessation⁵⁵ and may itself be an effective intervention compared to standard care.

3. Text messaging (TM): Brief advice + 12 week personalized, tailored text messaging program.

Rationale: Text messaging shows promise as an intervention to help smokers to quit.^{8,56} However, it has not been well tested among primary care patients. Text messaging may connect those primary care smokers who do not access currently available treatment services like telephone counseling or prescribed medication with assistance outside of the clinic office.

4. Text messaging and nicotine replacement therapy (TM+NRT): Brief advice + 12 week personalized, tailored text messaging program + 2 weeks of nicotine patches and/or lozenges mailed to subject.

Rationale: As above, in order to test the effect of text messaging on medication adherence, we need to have treatment groups receiving medication and medication plus text messaging. Text messaging has been shown to increase medication adherence in other conditions³⁴⁻³⁷ and medication adherence is suboptimal among users of smoking cessation medications.^{38,39,41} Integrating text messaging within healthcare systems offers opportunities to coordinate with pharmacotherapy and this 4 group design allows us to test the effect of text messaging alone on smoking outcomes and the effect of text messaging on NRT use.

We will use stratified block randomization. We will stratify by practice and readiness to quit in the next 30 days. We will use variable block sizes. Subjects will be randomized 1:1:1:1.

After verbal consent and chart review by the PCP. Randomized enrollees will be asked to complete a baseline telephone survey. After completion of the baseline survey, participants will be mailed a \$20 gift card.

Following the telephone survey, smokers randomized to the text messaging arms (TM and TM+NRT) will have their mobile numbers, and first names entered into the MobileCommons web-based platform. The program will be tailored to readiness to quit and user-entered quit date and personalized with individual's first name.

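### The pooled text-messaging comparison carries no NRT term: a mild loss of power, bias only under one particular pattern of loss, and a free improvement to make

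*Combined protocol and SAP*

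**What the plan says.** Data analysis (section VI) treats the four arms as a 2x2 factorial: "We will first test for interaction between the NRT and TM interventions". If none is detected, "we will test the effect of text messaging using both TM and TM+NRT arms compared to BA and NRT arms". If one is detected, the contrast changes: "If interaction is present, we will compare the TM arm to BA for our primary analysis".

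The method for the primary outcome is given as "comparing the primary outcome using chi-square analysis or multiple logistic regression analysis if any baseline factor is significantly imbalanced by group". For secondary outcomes the plan names chi-square or t-tests, with logistic or linear regression if groups are imbalanced. It does not spell out pooling there, but the Sample size text for Hypotheses 3 to 5 sets BA and NRT together against TM and TM+NRT.

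On allocation, section IV.c says "Subjects will be randomized 1:1:1:1". The same section says of mailed NRT alone that it "may itself be an effective intervention compared to standard care". Of missing data, the plan says only "The primary outcome analysis will be conducted as intention-to-treat". The power statements remove 25% for loss, and no rule for missing outcomes is given.

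**The concern.** NRT assignment is a randomised factor, not a baseline factor. The trigger for regression therefore cannot bring it in, and no stated version of the pooled test carries it. The preceding interaction test asks whether the TM effect differs by NRT, not whether NRT shifts the outcome. When the product term is dropped, the NRT main effect would normally stay in the model.

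Two things are at stake. First, variation due to NRT stays in the null variance of the collapsed test, which makes it conservative. Second, NRT is balanced across TM only among those randomised. If the participants analysed are no longer balanced, part of the NRT effect can pass into the TM estimate. The pilot means to supply effect estimates for later studies, so an avoidable distortion would carry forward.

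**Working it through.** **Inputs from the plan.** 50 per arm, 25% loss, so 37.5 analysed per arm and 75 per pooled side; alpha 0.05 (two-sided assumed).

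**Assumptions, because the plan gives no figures.** Quit-attempt rates, the size of the NRT effect, and retention by arm.

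**The plan's own pooled figures.** Two-sided, normal approximation, 75 per side:
- Hypothesis 3 (6% v 22%): 81.3%, stated 80%.
- Hypothesis 4 (difference 0.8 days, SD 2): 68.8%, stated 68%.
- Hypothesis 5 (difference 3 cigarettes, SD 7): 74.7%, stated 75%.

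These reproduce, so the pooled contrast with 75 per side is what was powered. On the Hypothesis 3 inputs, stratifying on NRT raises power from 81.3% to 81.5% at an NRT odds ratio of 1.5, from 81.5% to 81.8% at 2, and from 81.7% to 82.5% at 3.

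**Power for quit attempts.** With equal arms the risk difference d is the same number either way, and its true SE is the square root of [sum of p(1-p) over the four arms / (4 x 37.5)]. Only the null SE differs:
- collapsed: square root of [2 x P(1-P)/75], where P is the overall rate;
- stratified: square root of [2 x M/75], where M is the mean over NRT levels of the pooled p(1-p).

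Power = Φ[(d - 1.96 x null SE) / true SE].

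Example: BA 40%, NRT +20 points, TM +20 points, giving arms of 40, 60, 60 and 80%.
- True SE = √(0.88/150) = 0.0766.
- Collapsed null SE = √(2 x 0.24/75) = 0.0800; power Φ(0.564) = 71.4%.
- Stratified null SE = √(2 x 0.23/75) = 0.0783; power Φ(0.607) = 72.8%.

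| Assumed NRT effect | TM +15 points: collapsed / stratified | TM +20 points: collapsed / stratified |
|---|---|---|
| 10 points | 45.1% / 45.5% | 69.7% / 70.0% |
| 20 points | 45.8% / 47.5% | 71.4% / 72.8% |
| 30 points | 47.3% / 51.4% | 74.4% / 77.8% |

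**Type I error, no TM effect, NRT moving 40% to 60%.** Collapsed null SE = √(2 x 0.25/75) = 0.0816; true SE = √(2 x 0.24/75) = 0.0800. Rejection = 2Φ(-1.96 x 0.0816/0.0800) = about 4.5%.

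**Continuous outcome (Hypothesis 5).** Assume NRT also shifts cigarettes per day by 3. Between-NRT variance is 3²/4 = 2.25 of 49, so the within-level SD is √46.75 = 6.84. The SEs are 7√(2/75) = 1.143 collapsed and 6.84√(2/75) = 1.117 within levels. Power is Φ[(3 - 1.96 x 1.143)/1.117] = 75.2% collapsed and Φ[3/1.117 - 1.96] = 76.6% adjusted.

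**An outcome driven by NRT.** Use of at least one evidence-based treatment counts NRT, which two arms are mailed. At assumed rates of 30% without and 85% with mailed NRT, M = (0.21 + 0.1275)/2 = 0.169 against 0.575 x 0.425 = 0.244, so stratifying removes 31% of the null variance. For a 10-point gain, power is about 20% collapsed and 33% stratified. The collapsed test's type I error is about 2%.

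**Loss.** Under complete-case analysis with no TM effect, the spurious TM difference is (NRT share on the TM side - NRT share on the no-TM side) x NRT effect. For an assumed 20-point NRT effect:

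| Retention BA / NRT / TM / TM+NRT | NRT share: TM side, no-TM side | Spurious difference |
|---|---|---|
| 65 / 85 / 65 / 85% | 56.7%, 56.7% | 0 |
| 85 / 85 / 65 / 65% | 50%, 50% | 0 |
| 65 / 75 / 75 / 85% | 53.1%, 53.6% | -0.1 points |
| 70 / 80 / 80 / 70% | 46.7%, 53.3% | -1.3 points |
| 60 / 80 / 80 / 80% | 50%, 57.1% | -1.4 points |
| 85 / 65 / 65 / 85% | 56.7%, 43.3% | +2.7 points |
| 90 / 60 / 60 / 90% (extreme) | 60%, 40% | +4.0 points |

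For the 85/65/65/85 pattern the collapsed test rejects with probability Φ(-2.00 + 0.0267/0.0800) + Φ(-2.00 - 0.0267/0.0800) = about 6%. Simulations with whole-number arms gave 6.2% and 6.8%. The NRT-stratified estimate has bias of about 0 and rejects about 5% of the time in these scenarios.

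**The case against.** Four stronger readings are tempting, and the documents do not support them.

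- **The plan ignores NRT altogether.** It does not. The interaction test comes first and uses the NRT factor, and the fallback contrast (TM v BA) is not collapsed, so the point does not arise there. What is missing is an NRT term in one step.
- **The collapsed test is invalid.** With equal arms it errs on the conservative side, and neither the risk difference nor its true SD changes. On quit attempts the gain is so small that small-sample discreteness can hide it: one simulation at a 10-point NRT effect gave 70.8% collapsed and 69.9% stratified.
- **Any unequal loss across the four arms biases the answer.** Loss that differs by NRT alone or by TM alone gives zero bias. Retention must depend on the TM-by-NRT combination, NRT must affect the outcome, and missing outcomes must be dropped. The plan states none of these three, though it does expect NRT to help. Quit attempts reported at earlier follow-ups also count, and up to 10 contact attempts are made per assessment, so fewer than 25% may lack the primary outcome.
- **The treatment-use figures show the typical cost.** They rest on assumed rates, and they are large because mailed NRT itself counts towards that outcome. That is mainly a problem of outcome definition, and the gain shrinks once it is solved.

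It is also fair to say that stratifying is no remedy for missing data. If missing outcomes were counted as no attempt, the 85/65/65/85 pattern with 40% and 60% rates gives (0.34 + 0.39)/2 = 36.5% without TM and (0.26 + 0.51)/2 = 38.5% with TM. That is a spurious 2.0 points, which an NRT stratum does not remove.

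All of this limits the size of the point. It does not supply the missing NRT term or give a reason to leave it out.

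**Conclusion.** The point holds as a minor one. No stated main-effect test of TM includes the randomised NRT factor, although section IV.c expects mailed NRT to help smokers quit. On quit attempts the cost is roughly 0 to 4 power points for assumed NRT effects up to 30 points, and at most 0.8 points on the plan's own Hypothesis 3 rates at NRT odds ratios up to 3.

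Bias is conditional. It is about 1 to 3 points in plausible scenarios with an assumed 20-point NRT effect, complete-case analysis and retention that differs by the TM-by-NRT combination. Otherwise it is zero or close to it. The 2.7-point case compares with a standard error of about 8 points.

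The quit-attempt rates, NRT effects, retention patterns and two-sided testing are assumptions. The absence of an NRT term is read directly from the plan.

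**What to change.** Add one sentence to Data analysis: every pooled TM comparison will be stratified on, or adjusted for, NRT assignment, regardless of observed balance.

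- Binary outcomes: a Mantel-Haenszel risk difference or ratio with its confidence interval, and the CMH test. If logistic regression is used because a baseline factor is imbalanced, it should carry the NRT indicator too.
- Days not smoked and cigarettes per day: a linear model with an NRT indicator.
- Secondary outcomes: say explicitly that the pooled contrast is the one used.

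The cost is one sentence and one degree of freedom; no further data are needed. The same sentence could say how the randomisation factors ("We will stratify by practice and readiness to quit in the next 30 days") will be handled. A rule for missing outcomes is still needed separately, because adjusting for NRT does not deal with outcome-related loss within arms.
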